17.4.5.8 Safety Analyses

An AE will be considered a TEAE if:

- 1) The AE was not present before the first dose in Study MT-1186-A02 but started after administration of the first dose of study drug in Study MT-1186-A02, or
- 2) The AE was present before the first dose in Study MT-1186-A02 but increased in severity following administration of the first dose of study drug in Study MT-1186-A02.

TEAEs will be coded using the latest available version of MedDRA and will be summarized in incidence tables by System Organ Class (SOC) and Preferred Term (PT). The numbers and proportions of subjects with TEAEs will be calculated for each treatment group by SOC and PT.

The following summaries will be presented:

- TEAEs by SOC and PT
- TEAEs by SOC, PT, and severity
- TEAEs by SOC, PT, and drug relationship
- TEAEs leading to discontinuation of study drug by SOC and PT
- TEAEs leading to death by SOC and PT
- TEAEs related to study drug by SOC, PT, and severity
- TEAEs of Peripheral Neuropathy Standardized MedDRA query by SOC and PT
- Serious TEAEs by SOC and PT
- Serious TEAEs related to study drug by SOC and PT

For each of the summaries, multiple occurrences of the same event within a subject will be counted once in the summaries by SOC and PT; multiple occurrences of the same event within a subject will be counted once in the maximum severity category (severe>moderate>mild) and/or maximum study drug relationship category (reasonable possibility/no reasonable possibility). If severity or relationship is found to be missing, the most severe occurrence will be imputed for that summary.

All AEs for each subject, including multiple occurrences of the same event, will be presented in full in a comprehensive listing including subject number, severity, seriousness, action taken, outcome, relationship to treatment, onset/stop date, and duration.

Duration of the AE and time to the AE occurrence from start of edaravone will be calculated and presented in days (duration = AE stop date - AE start date + 1 and time to AE occurrence = AE start date - The first administration date of study drug + 1).

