8.3.1.3. Concomitant Medication

Definition of concomitant medications in the protocol

Concomitant medication is defined as any medication, other than the study drug, which is taken after the first dose administration in Study MT-1186-A02, including prescription, herbal and over-the-counter medications. All concomitant medications taken while the subject is participating in the study will be recorded in the eCRF. All medications will be classified using the Anatomical Therapeutic Chemical (ATC) classification codes and preferred drug names from the World Health Organization Drug Dictionary (WHO-DD, version from September 2019).

Concomitant medications, except for riluzole, will be summarized by ATC level 2 categories and preferred name. Riluzole administration will be summarized separately.

Rules to determine concomitant medications

Medications with a stop date before the first date of study drug dosing in MT-1186-A02 will be considered prior medications. Medications with start date or stop date on or after the first date of study drug dosing in MT-1186-A02 or ongoing up to week 48 in MT-1186-A04 will be considered concomitant medications.

If the medication start date is incomplete, then it will be imputed as follows for the purpose of determining concomitant use:

• If the start date is completely missing, the start date will be equal to the first dose date.

However, if the stop date is not missing and is before the first dose date, then the stop date will be used instead.

Mitsubishi Tanabe Pharma America, Inc.

- If the start day is missing, the first day of the month will be used.
- If the start day and month are missing, then the first day of the first month (January) will be used.

If the medication stop date is partial, then it will be imputed as follows for the purpose of determining concomitant use:

- If the stop date is completely missing and the medication is not ongoing, the stop date will be equal to the last dose date or date of completion/withdrawal, whichever is the latest.
- If the stop day is missing, the last day of the month will be used.
- If the stop day and month are missing, then the last day of the last month (December) will be used.

Integration of continued concomitant medications from MT-1186-A02 to MT-1186-A04:

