8.3.3. Safety Measures

8.3.3.1. Adverse Events

An AE is any untoward medical occurrence in a subject or clinical investigation subject administered a pharmaceutical product that does not necessarily have a causal relationship with this IMP. An AE can therefore be any unfavorable and unintended sign (including an abnormal laboratory finding, for example), symptom, or disease temporally associated with the use of an IMP, whether or not considered related to the IMP.

Adverse events will be coded according to the MedDRA version 23.0

- Adverse Events will be classified for Treatment Emergent AEs (TEAEs) if at least one of the following conditions is met:
 - The AE was not present before the first dose in Study MT-1186-A02 but started after administration of the first dose of study drug in Study MT-1186-A02, or,
 - The AE was present before the first dose in Study MT-1186-A02 but increased in severity following administration of the first dose of study drug in Study MT-1186-A02.

Mitsubishi Tanabe Pharma America, Inc.

Integration of continued AEs from MT-1186-A02 to MT-1186-A04:

TEAE's from MT-1186-A02 will be integrated into TEAE's from the current MT-1186-A04 study in order to be able to analyze the continued safety profile. If AE in MT-1186-A04 met all following conditions, the AE in MT-1186-A02 and MT-1186-A04 will be merged into a single AE.

- Onset date of AE in MT-1186-A02 = Onset date of AE in MT-1186-A04
- Lowest level terms (LLT) of AE in MT-1186-A02 = LLT of AE in MT-1186-A04
- "Was this event ongoing at the end of MT-1186-A02?" in MT-1186-A04 CRF = "Yes" Then, for AE analysis, AE End date and Outcome data in MT-1186-A04 CRF data rather than MT-1186-A02 CRF data will be prioritized and analyzed.

Handling Partial Dates:

The handling of partial dates in study MT-1186-A02 were provided in a designated SAP for this study. The following are the rules for partial dates handling for TEAE's newly captured in MT-1186-A04 study:

- AE with a missing start time, but with a start date equal to the date of first dose of study treatment in MT-1186-A04 will be considered treatment-emergent.
- If the AE start date is incomplete, it will be imputed as follows for the purpose of determining TEAE:

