 - o If the start date is completely missing, the start date will be equal to the date of the first dose date of study drug in MT-1186-A04. However, if the stop date is not missing and is before the date of the first dose of study drug in MT-1186-A02, then the stop date will be used instead, and the AE will not be considered as TEAE.
 - o If the start day is missing, but the month and year are not missing and are equal to the month and year of the first study dose in MT-1186-A02, then this event will be considered as TEAE.
 - o If the start day and month are missing, then the first day of the first month (January) will be used.
- If an AE stop date is incomplete, it will be imputed as follows for the purpose of determining AE duration:
 - o If the AE stop date is completely missing, then the stop date will be equal to the subject's last observed date in MT-1186-A04.
 - If the Stop day is missing, but the month and year are not missing and are equal to the month and year of the last observed date in MT-1186-A04, then stop date will be equal to last observed date.

Mitsubishi Tanabe Pharma America, Inc.

- o If the start day and month are missing, then the first day of the first month (January) will be used.
- Adverse Events will be classified for Adverse Drug Reactions (ADR) if an AE is valuated as having causally related to the investigational product with "a reasonable possibility"

Serious Adverse Events

A serious Adverse Event (SAE) is defined as any untoward medical occurrence that at any dose:

- Results in death;
- Is life-threatening;
- Requires hospitalization or prolongation of existing hospitalization;
- Results in persistent or significant disability or incapacity;
- Is a congenital anomaly or birth defect;
- Is an important medical event.

All SAEs occurring from the time written ICF is obtained from a subject until the end of the Safety Follow-up period or the withdrawal of the subject from the study must be reported to the Sponsor/CRO. All SAEs and AESI must also be entered in the AE section of the eCRF within 24 hours.

Duration of Adverse Events

After the integration of TEAEs from MT-1186-A02 into TEAEs from MT-1186-A04, the following rules will be applied to calculate duration of TEAE's:

Duration of the AE and time to the AE occurrence from start of study drug in MT-1186-A02 will be calculated and presented in days

- Duration = AE stop date AE start date + 1

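### The rule for a year-only adverse event stop date in SAP 8.3.3.1 is a copy of the start-date rule, so it is either wrong or absent

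*SAP*

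**What the plan says.** SAP 8.3.3.1, under Handling Partial Dates, limits its scope at the outset: "The following are the rules for partial dates handling for TEAE's newly captured in MT-1186-A04 study". Partial dates in MT-1186-A02 are left to that study's own SAP.

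Two lists follow.

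- **Start dates.** The stated purpose is treatment-emergent status: "If the AE start date is incomplete, it will be imputed as follows for the purpose of determining TEAE". The last item sends a start date with unknown day and month to 1 January.
- **Stop dates.** The stated purpose is duration: "If an AE stop date is incomplete, it will be imputed as follows for the purpose of determining AE duration". There are three items:
  1. "If the AE stop date is completely missing, then the stop date will be equal to the subject's last observed date in MT-1186-A04".
  2. When only the day is unknown, and the recorded month and year match those of the subject's final observation, the date of that final observation is taken.
  3. "If the start day and month are missing, then the first day of the first month (January) will be used". This repeats the closing item of the start-date list word for word.

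Protocol 17.4.5.8 gives the formula "duration = AE stop date - AE start date + 1", and SAP 8.3.3.1 uses the same definition. For medication stop dates, SAP 8.3.1.3 has "If the stop day and month are missing, then the last day of the last month (December) will be used".

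**The concern.** The third stop-date item runs against the other two, which both impute a late date. It also runs against the convention that the same SAP adopts for medication stop dates. Nothing in the list requires the imputed stop date to fall on or after onset, so the rule can produce durations that are impossible.

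AE duration is a specified output. SAP 8.3.3.1 says it will be calculated and presented in days, and the comprehensive AE listing in Protocol 17.4.5.8 includes it. A programmer following the text must either output impossible values or make an undocumented choice.

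**Working it through.** The plan states no figure on this point, so there is none to reproduce. The check is date arithmetic on the plan's own formula.

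**Inputs**
- Duration = stop - start + 1 (Protocol 17.4.5.8; SAP 8.3.3.1).
- Imputed stop = 1 January of the recorded year (third stop-date item, applied by position).
- Comparator = 31 December of the recorded year (SAP 8.3.1.3).
- Assumption: onset is fully known. Every onset day in the year was tried.

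**Same-year onset.** Let onset fall on day k of the year. With stop on day 1, duration = 1 - k + 1 = 2 - k. With stop on day 365, duration = 365 - k + 1 = 366 - k.

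| Onset (2022) | k | 1 January rule | 31 December rule |
|---|---|---|---|
| 1 January | 1 | 1 | 365 |
| 2 January | 2 | 0 | 364 |
| 10 March | 69 | -67 | 297 |
| 15 June | 166 | -164 | 200 |
| 31 December | 365 | -363 | 1 |

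Under the 1 January rule the stop precedes onset for 364 of 365 onset days (365 of 366 in a leap year). Duration is negative for 363 of 365 (364 of 366), zero for 2 January, and 1 only for 1 January. The minimum is -363 days (-364 in a leap year). Under the 31 December rule duration runs from 1 to 365 (366) and is never below 1.

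**Onset in an earlier year.** Onset 15 June 2022 with stop year 2023:
- 1 January 2023 gives 201 days.
- 31 December 2023 gives 201 + 364 = 565 days.

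The value is possible but is the shortest that the record allows.

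**Literal reading.** If the third item is taken at its word, it concerns start dates only. The stop-date list then covers a completely missing date and one case of a missing day, and says nothing about a year-only date.

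**Related gap.** The missing-day item applies only when the known month and year equal those of the last observed date. For any other month there is no rule.

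**The case against.** The strongest objection is that the item says start, not stop, so the 1 January reading is an inference from its place in the list. That stands, and it is why the point is that the rule is wrong or absent. Neither reading gives a workable rule. The sentence stands in both lists, and its second occurrence comes before the next main bullet, on adverse drug reactions. It therefore belongs to the stop-date list.

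Three stronger readings are tempting, and the documents do not support them.

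- **That the listing will show events ending before they began.** The imputation is stated to serve duration, and nothing says that imputed stop dates are printed. A zero or negative duration could appear; a displayed stop date before onset is not established.
- **That every AE with a year-only stop date gets an impossible duration.** The rules cover only events newly captured in MT-1186-A04. An earlier-year onset gives a positive value. If onset is also year-only in the same year, and its 1 January imputation is carried into duration, the result is 1 day.
- **That the safety comparison is affected.** The planned tables in SAP 9.3.1 are subject counts and proportions, event counts, and event rates per 100 person-years of drug exposure. None uses AE duration.

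It is also fair to say that year-only stop dates may be rare. Protocol 15.6 asks for the date and time of resolution, and Protocol 16.1 to 16.3 provide for data review and queries. The documents give no count either way.

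**Conclusion.** The point holds as a drafting error in an operative derivation rule. By position, the rule gives a zero or negative duration for any known same-year onset after 1 January, and the shortest possible duration for an earlier-year onset. Read literally, the year-only rule is missing.

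The consequence is minor. It reaches only the presented duration of AEs newly captured in MT-1186-A04 whose stop date is known to the year alone. Treatment-emergent status is settled by the start-date rules, and no incidence table or efficacy analysis depends on AE duration. The arithmetic assumes a known onset date. How many events are affected cannot be judged from the documents.

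**What to change.** Change only the second occurrence of the sentence, in the stop-date list; the start-date list stays as it is. Proposed text:

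> If the stop day and month are missing, take 31 December of the recorded year, or the last observed date in MT-1186-A04 if that falls earlier in the same recorded year. The imputed stop date may not precede the AE start date.

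The cap must stay within the recorded year. Simply taking the earlier of 31 December and the last observed date could move an event recorded as ending after follow-up into an earlier year. That is possible because Protocol 15.8 has events followed until they resolve or stabilise.

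In the same edit, add:

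> If only the stop day is missing and the month is not that of the last observed date, take the last day of the recorded month.

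The cost is two or three SAP sentences and a small change to the duration derivation. No new data are needed. SAP section 2 allows updates before final database lock and otherwise requires deviations to be described and justified in the clinical study report.

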8.3.3.2. Columbia Suicide Severity Rating Scale (C-SSRS)

The C-SSRS is a clinician-rated instrument that captures the occurrence, severity, and frequency of suicide-related ideations and behaviors during the assessment period. Suicidal ideation is classified on a 5-item scale: 1 (wish to be dead), 2 (nonspecific active suicidal thoughts), 3 (active suicidal ideation with any methods [not plan] without intent to act), 4 (active suicidal ideation with some intent to act, without specific plan), and 5 (active suicidal ideation with specific plan and intent). The C-SSRS also captures information about the intensity of ideation, specifically the frequency, duration, controllability, deterrents, and reasons for the most severe types of ideation. Suicidal behavior is classified on a 5-item scale: 0 (no suicidal behavior), 1 (preparatory acts or behavior), 2 (aborted attempt), 3 (interrupted attempt), and 4 (actual attempt). More than 1 classification can be selected provided they represent separate episodes. For actual attempts only, the actual or potential lethality is classified for the initial, most lethal, and most recent attempts.

The sever level of suicidal ideation 5 items from low to high:

- 1: Wish to be dead
- 2: Non-specific active suicidal thoughts
- 3: Active suicidal ideation with any methods (not plan) without intent to act
- 4: Active suicidal ideation with some intent to act, without specific plan
- 5: Active suicidal ideation with specific plan and intent

The sever level of suicidal behavior 5 items from low to high:

- 1: Preparatory Acts or Behavior
- 2: Aborted Attempt

Mitsubishi Tanabe Pharma America, Inc.

- 3: Interrupted Attempt
- 4: Actual Attempt
- 5: Suicidal Behavior

8.3.3.3. Laboratory Tests

Hematology tests will include: Red blood cell count, hemoglobin, hematocrit value, white blood cell count with differential and platelet count.

Blood Chemistry will include: Albumin, Total protein, aspartate aminotransferase (AST), alanine aminotransferase (ALT), lactate dehydrogenase (LDH), alkaline phosphatase (ALP), total bilirubin, direct bilirubin, c-reactive protein (CRP), creatine kinase (CK), total cholesterol, triglycerides, blood urea nitrogen (BUN), bicarbonate, serum glucose, serum creatinine level, uric acid, sodium (Na), potassium (K), chloride, calcium (Ca), cystatin-C and Vitamin B6.

Note: In addition, GGT will be obtained in only Japan country.

Qualitative urinalysis will include: Protein, glucose, occult blood, white blood cells, urobilinogen, and bilirubin.

Pregnancy test (WOCP only): For women subjects with Childbearing Potential only, serum beta-human chorionic gonadotropin (hCG) level or urine dipstick will be conducted.

Laboratory values below the limit of quantification

Laboratory values below 1/2 LLOQ (lower limit of quantification) will be used for BLQ (below the limit of quantification) for data summary statistics.

Handling of Reference Values and Indeterminate Values for Clinical Laboratory Test Parameters

If laboratory test value or its reference is indeterminate due to a problem with the test sample, then this value will be handled as a missing value.

Criteria for Potentially Clinically Significant Values (PCSV for laboratory):

The following criteria will be defined 8,9

Chemistry

- ALT $>= 3 \times \text{Upper Limit of Normal Range (ULN)}, 5 \times \text{ULN}, 10 \times \text{ULN}, 20 \times \text{ULN}$
- AST $>= 3 \times ULN$, $5 \times ULN$, $10 \times ULN$, $20 \times ULN$
- ALT and/or AST >= 3 \times ULN, $5\times$ ULN, $10\times$ ULN, $20\times$ ULN
- Total Bilirubin $\geq 2 \times ULN$

Mitsubishi Tanabe Pharma America, Inc.

- ALP >400 U/L
- ALT or AST > $3 \times ULN$ with Total Bilirubin > $1.5 \times ULN$
- ALT or AST $> 3 \times ULN$ with Total Bilirubin $> 2 \times ULN$
- Hy's law (ALT or AST > $3 \times ULN$ and ALP < $2 \times ULN$ and Total Bilirubin >= $2 \times ULN$)
- LDH $>= 3 \times ULN$
- BUN >= 30 mg/dL
- Serum Creatine >= 2.0mg/dL
- Uric acid Male >10.0 mg/dL, Female >8.0 mg/dL
- $CK \ge 3$ x upper limit of normal
- Chloride (Low) $\leq 90 \text{ mEq/L}$
- Chloride (High) ≥ 118 mEq/L
- Potassium (K) (Low) <3.0 mmol/l
- Potassium (K) (High) >5.5mmol/1
- Sodium (Na) (Low) <130mmol/1
- Sodium (Na) (High) ≥ 150 mmol/l
- Calcium (Ca) (Low) <7.0 mg/dL
- Calcium (Ca) (High) ≥ 12 mg/dL
- Concurrent Hepatic Abnormality;
- ALT or AST > $3 \times$ ULN with Total Bilirubin > $1.5 \times$ ULN
- ALT or AST > $3 \times$ ULN with Total Bilirubin > $2 \times$ ULN
- Hy's law (ALT or AST > $3 \times$ ULN and ALP < $2 \times$ ULN and Total Bilirubin >= $2 \times$ ULN)

Hematology

- Hematocrit:
 - Male ≤ 37 % and decrease of ≥ 3 percentage points from baseline,
 - o Female <=32 % and decrease of ≥ 3 percentage points from baseline
- Hemoglobin:
 - o Male ≤ 11.5 g/dL,
 - o Female ≤ 9.5 g/dL
- White blood count (Low) $\leq 2800/\text{mm}3$
- White blood count (High) ≥ 16,000/mm3
- Neutrophils Absolute count < 1,000/mm3
- Platelet count (Low) $\leq 100,000/\text{mm}$ 3
- Platelet count (High) ≥ 700,000/mm3

Mitsubishi Tanabe Pharma America, Inc.

8.3.3.4. 12-Lead ECG

A 12-lead ECG will be performed after the subject has rested for at least 5 minutes in a supine position. The ECG will include the following numerical measurements: HR, R wave to R wave (RR) interval, heart rate, QRS, QT, QTcB, and QTcF. The Investigator will perform an overall evaluation of the ECG for safety purposes and the recording will be reported as 'normal', 'abnormal CS', or 'abnormal NCS'

The RR, QTcF and QTcB will be calculated using the below formulas, regardless if collected in CRF.

- RR (msec) will be calculated as {60 / heart rate (beats/min)} *1000 and reported to integer.
- QTcF (msec) and QTcB (msec) will be calculated as {QT (sec) / RR (sec) ^ (1/3)} * 1000 and {QT (sec) / RR (sec) ^ (1/2)} *1000 respectively and reported to integer.

Criteria for Potentially Clinically Significant Values (PCSV for 12-Lead ECG):

- HR at post-baseline <=50 bpm and decrease from baseline >=20 bpm
- HR at post-baseline >=120 bpm and increase from baseline >=20 bpm
- PR at post-baseline >=220 msec and increase from baseline >=20 msec
- QRS at post-baseline >= 120 msec and QRS at baseline < 120 msec
- Baseline OTc <=450 msec and QTc >450 msec at post-baseline
- Baseline QTc <=480 msec and QTc > 480 msec at post-baseline
- Baseline QTc <=500 msec and QTc > 500 msec at post-baseline
- Change from baseline at post-baseline in QTc > 30 msec
- Change from baseline at post-baseline in QTc > 60 msec

8.3.3.5. Vital Signs

The following measurements will be collected: systolic and diastolic blood pressure, heart rate (e.g., beats per minute), respiratory rate, and axillary, oral, temporal [skin-based], or tympanic body temperature) (eg, Celsius). The Investigator will perform an overall evaluation for safety purposes and the recording will be reported as 'normal', 'abnormal clinically significant (CS)', or 'abnormal not clinically significant (NCS)'.

Criteria of Potentially Clinically Significant Values (PCSV) for Vital⁷ Signs

The following criteria to determine risk for PCSV for Vital signs are defined:

- HR at post-baseline <=50 bpm and decrease from baseline >=15 bpm
- HR at post-baseline >=120 bpm and increase from baseline >=15 bpm
- SBP at post-baseline <=90 mmHg and decrease from baseline >=20 mmHg
- SBP at post-baseline >=180 mmHg and increase from baseline >=20 mmHg
- DBP at post-baseline <=50 mmHg and decrease from baseline >=15 mmHg
- DBP at post-baseline >=105 mmHg and increase from baseline >=15 mmHg

Mitsubishi Tanabe Pharma America, Inc.

